- To describe the adverse events encountered, their severity according to ASGE standards and their management.
- To describe the time elapsed between the procedure and the initial oral intake.
- To describe the evolution of the oral intake during the first month after the procedure
- To assess the impact of the operators experience on procedure times, adverse events and technical issues.
- To assess the impact of the procedure on the quality of life of the participating patients.

4. Design

Prospective, multicenter case-series

5. Methods

Study population

All consecutive patients over 18 years of age submitted to any of the participating center's endoscopy units to receive a nasobiliary drain assisted EUS-GE for unresectable malignant GOO are eligible to participate in this study.

Inclusion and exclusion criteria

Inclusion criteria:

- Unresectable malignant gastric outlet obstruction
- Scheduled placement of a nasobiliary drain assisted EUS-GE
- Age >18 years.

Exclusion criteria:

- Previous gastroduodenal surgery
- Previous endoscopic or surgical treatment for gastric outlet obstruction
- Simultaneous malignant biliary obstruction requiring endoscopic treatment
- Unable to understand the questionnaires
- Distal bowel obstruction
- Ascites grade 2 or superior
- Uncorrectable coagulation disorders (INR>1,5) or severe thrombocytopenia (<50000 platelets/mm3).

Definitions of the outcomes employed to assess primary and secondary variables

1. Technical success: Dichotomous variable. Defined as a correct placement of the LAMS, with one flange inside the gastric cavity and the other one in the small bowel. It should be confirmed endoscopically or fluoroscopically

2. Clinical success: Dichotomous variable. Defined as a GOOSS ≥ 2 . It will be assessed at days +7 and +30.
- 3.
4. Recurrent GOO: Dichotomous variable. In patients achieving clinical success in day +7, recurrent GOO is defined as the development of nausea and vomiting and/or a GOOSS < 2 .
5. Persistent GOO: Dichotomous variable. Continuing nausea, vomiting, and inability to tolerate PO intake up to or occurring within 2 weeks after the procedure.
6. Major complications: life-threatening or severe complications requiring treatment and/or hospitalization (The adverse event severity will be graded according to the ASGE lexicon).
 - a. Early major complications: complications occurring within 7 days after the intervention.

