identifying the target, a lumen apposing metal stent (Axios, Boston Scientific, Massachusetts) is deployed across the gastric and bowel using its electrocautery enhanced deployment device.

Post procedure

Oral liquid intake can be restarted 4h after the procedure in patients presenting no signs or symptoms suggesting any adverse event. Patients with an adequate tolerance might be discharged.

Follow-up

Clinical telephone interviews by an experienced research nurse will be held via telephone calls 1 day, 7 days and 30 days after the procedure. Oral intake and adverse events will be assessed every visit. Thirty days after the procedure a second evaluation of the EORTC-QLQ-C30 will be performed.

Sample size

Although EUS-GE is a rather infrequent procedure, we aim at including at least 5-10 procedures/endoscopist, in order to present each operator's *modus operandi*. Thus, recruitment will be active until a minimum of 5 procedures/endoscopist is reached or until a total sample size of 50 patients is reached, with at least 4 endoscopists including >5 procedures). To assess the secondary endpoint of the quality of life, previously published papers assessing QoL in patients with unresectable malignant GOO using the EORTC-QLQ-C30 reported mean global health status scores of 36.6 (SD: 20.1) and 45 (SD: 20.3) before treatment. To detect at least a 14-points change

with a 5% alfa risk and an 80% power, 33 subjects were estimated to be needed. Assuming a 20% of losses, 40 patients were required.

Adverse events monitoring

Adverse events (AE) are defined as any event preventing from completing the procedure, causing or lengthening a hospital admission or conditioning further interventions or unscheduled hospital or out-patient clinic visits. According to the time of diagnosis, they are classified as intraprocedure (diagnosed in the endoscopy unit during or immediately after the procedure), postprocedure (diagnosed in the 7 days following the procedure) or delayed (diagnosed beyond the first 7 days after the procedure). Causal relationship will be categorized into definitive (clearly related), probable (probably related), possible (might be related) or unlikely (there are other more likely causes). Severity will be assessed according to the ASGE recommendations

Consequence	Severity			
	Mild	Moderate	Severe	Fatal
Stop (or not even starting) a procedure	x			
Post-procedure out-patient visit	x			
Unplanned respiratory support during the procedure		x		

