Unplanned hospital admission for 3 nights or less	x			
Unplanned hospital admission for 4-10 nights		x		
Unplanned hospital admission for 11 or more nights			x	
Intensive Care Unit admission for 1 night		x		
Intensive Care Unit admission for 2 or more nights			x	
Blood transfusion		x		
Endoscopic procedure		x		
Radiologic procedure		x		

	Severity			
Consequence	Mild	Moderate	Severe	Fatal
Surgical procedure			x	
Permanent disability			x	
Death				x

The principal investigator at each center is responsible of communicating all adverse events (all severe or fatal adverse events, regardless of the causal relationship and at least possible for moderate or mild events) to the principal investigator.

Data retrieval

Data were collected and managed using the SEED Research Electronic Data Capture tool (REDCap), a secure, web-based application created to support data capture for research studies providing semiautomatic data quality control (9). Patient-related and procedural data were included by the local investigators at stent deployment. Patients will be identified with a unique code. The database is password protected. Only the investigators have access to the database.

Local follow-up was performed according to each center's protocols. Regardless of the local follow-up, all patients underwent a centralized follow-up via telephone calls by an experienced research nurse, at inclusion, 1, 7 and 30 days after stent deployment. The EORTC-QLQ-C30 questionnaires were administered at the inclusion and at the 30 days telephone visits. Only in case the patient was admitted at the principal investigator center and preferred a personal interview, were the questionnaires administered in a face-to-face interview. Oral intake was evaluated 1, 7 and 30 days after the procedure.

6. Statistical analysis

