Categorical variables were reported as percentages. Normally distributed continuous variables were reported as the mean with the standard deviation values. Non-normally distributed continuous variables were reported as the median and interquartile range. The EORTC QLQ-C30 descriptive analysis was performed with a specifically programmed Stata command (10). Variables regarding the procedure step by step analysis will only undergo a descriptive analysis. Differences between the different outcomes of the EORTC-QLQ-C30 will be assessed using linear mixed models with fixed effects for baseline values, and interaction with oncological treatment. The statistical analysis will be performed using the Stata package (StataCorp. 2013, College Station, Texas).

7. Ethics

Benefit risk assessment

Patients taking part in the study will not gain any personal benefit. We consider taking part in the study does not increase the risks associated to the procedure. The study is purely observational; data retrieval will not be performed by the operator. Thus, we consider the procedure in participating patients should defer from those EUS-GE performed in other patients. Follow-up will be performed via telephone calls, so the patient will not have to travel to take part. The procedure associated risk are well documented in the published literature, with an adverse event risk of 5%. The main risk is a hollow viscus perforation, followed by GI bleeding, and sedation associated procedures (aspiration pneumonia).

The study product, AXIOS™ (Boston Scientific) 20x10mm and 15x10mm lumen apposing metal stents, was originally designed to create internal drains for pancreatic fluid collections. Currently they are used in various other indications. Their deployment creating EUS-GE in patients presenting malignant unresectable GOO is increasing, both in Europe and in the United States, with various published case series.

8. Timeframe

First year

Recruitment of patients. Follow-up

Second year

Recruitment of patients. Follow-up (Recruitment will be active until the predetermined sample size of a minimum of 5 procedures/endoscopist is reached or until a total sample size of 50 patients is reached, with at least 4 endoscopists including >5 procedures).

Third year

Data análisis. Presentation in scientific meetings. Manuscript redaction.

9. Bibliography

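### The quality-of-life model names no term that estimates the 14-point change, and if baseline score is a covariate, the ordinary standard error for that change is generally too small

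*Combined protocol and SAP*

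**What the plan says.** The design is a single group (Section 4, "Prospective, multicenter case-series"). One secondary aim in Section 2 is "To assess the impact of the procedure on the quality of life of the participating patients". The questionnaire is given twice. Section 5, Follow-up, says "Thirty days after the procedure a second evaluation of the EORTC-QLQ-C30 will be performed", and Section 5, Data retrieval, agrees: "The EORTC-QLQ-C30 questionnaires were administered at the inclusion and at the 30 days telephone visits".

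Section 5, Sample size, sets the target for this aim: "To detect at least a 14-points change", "with a 5% alfa risk and an 80% power, 33 subjects were estimated to be needed". Its only variability inputs come from published studies that "reported mean global health status scores of 36.6 (SD: 20.1) and 45 (SD: 20.3) before treatment". It gives no SD of the change, no day-30 SD and no correlation between visits.

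Section 6 says that differences in the QLQ-C30 outcomes will be assessed with "linear mixed models with fixed effects for baseline values, and interaction with oncological treatment". That is all it says about the model.

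**The concern.** The sample size is built on a mean pre-post change, but the model sentence contains no term for it. A coefficient on baseline score is a slope. An interaction with oncological treatment modifies that slope or some term that is not named. An uncentred intercept is a prediction for a patient whose baseline score is zero. None of these is the mean change from inclusion to day 30.

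The analyst must therefore complete the model, and the choice affects the interval. In a single group there is no between-arm contrast for baseline adjustment to sharpen. When the target is the mean change itself, conditioning on baseline removes a part of the variance that belongs in the standard error. This is the only inferential analysis that Section 6 describes, so both the number reported as the answer and its error rate are at stake.

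**Working it through.** **Inputs.** From Section 5, Sample size: change of 14 points, 5% alpha, 80% power, 33 evaluable patients, pre-treatment SDs 20.1 and 20.3 (midpoint 20.2 used here). Assumed, because the documents give no figure: correlation r = 0, 0.5 or 0.7, and day-30 SD s1 = 16, 20.2 or 25.

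**1. The plan's own figure.** n = 2 × ((1.960 + 0.842) × 20.2 / 14)² = 32.7, so 33. This matches a calculation with r = 0, which the plan does not state. With r = 0.5 the same formula gives 16.3.

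**2. Standard errors if baseline score is a covariate.** Write s0 for the baseline SD and b = r × s1 / s0 for the slope of day-30 on baseline score. With complete pairs and no interaction term, each approach below gives the same point estimate (mean day-30 minus mean inclusion score). Only the variance differs.

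- True variance of the mean change: [(1 − b)² s0² + s1²(1 − r²)] / n.
- Completion A: both visits as rows, visit term, baseline covariate, patient random intercept. Baseline is on both sides of the equation, so the residual covariance within a patient is −(1 − b)² s0² / 4. A random intercept cannot be negative in variance and is held at zero. The model variance is then [(1 − b)² s0² / 2 + s1²(1 − r²)] / n.
- Completion B: day-30 score or change regressed on centred baseline. The model variance is s1²(1 − r²) / n, which treats the sample's baseline mean as fixed.

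Both fall short of the true variance by a multiple of (1 − b)² s0², so they equal it only when b = 1.

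Example, r = 0.5 and equal SDs: (1 − b)² s0² = 0.25 × 408.04 = 102.01 and s1²(1 − r²) = 0.75 × 408.04 = 306.03.
- True SE = √(408.04 / 33) = 3.52.
- A: √((51.0 + 306.03) / 33) = 3.29.
- B: √(306.03 / 33) = 3.05.

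**3. Results, n = 33, equal SDs, no true change.** With equal SDs the SE ratios are √((3 + r)/4) for A and √((1 + r)/2) for B. Type I error is from simulation with 100,000 runs per setting.

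| | r = 0 | r = 0.5 | r = 0.7 |
|---|---|---|---|
| True SE | 4.97 | 3.52 | 2.72 |
| A: SE short by | 13% | 6.5% | 3.8% |
| A: type I error (63 df) | 9.0% | 7.0% | 6.2% |
| B: SE short by | 29% | 13% | 8% |
| B: type I error (31 df) | 15.9% | 8.8% | 6.9% |
| Paired t: type I error (32 df) | 5.0% | 5.1% | 5.0% |
| 95% CI half-width: correct / A / B | 10.1 / 8.6 / 7.2 | 7.2 / 6.6 / 6.2 | 5.5 / 5.2 / 5.1 |

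The random intercept in A was estimated at zero in 100%, 98.1% and 90.4% of runs.

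**4. Sensitivity to the day-30 SD** (r = 0 / 0.5 / 0.7).
- SD 16: SE short by 17 / 12 / 10% in A and 38 / 25 / 21% in B.
- SD 25: SE short by 10 / 2.8 / 0.6% in A and 22 / 5.8 / 1.1% in B. At r = 0.7, b = 0.7 × 25 / 20.2 = 0.87, close to 1, and the loss is negligible.

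**5. The other reading.** If the phrase on baseline means the reference level of a visit factor, the model has two rows per patient, a visit effect and no baseline covariate. On complete pairs it returns the paired standard error unless the random intercept is estimated at zero. Trial fits at r = 0.5 gave a mean SE of 3.49 for both this model and the paired analysis. There is no shortfall of the kind in step 3.

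**The case against.** The strongest reply is that the shortfalls describe models that the plan does not state. That is right. Completions A and B are ours, nothing in the documents shows which one the investigators intend, and neither includes the oncological-treatment interaction that the plan names. The figures are a conditional illustration. A reader might infer from them that the plan's interval is invalid. The documents do not support that, because the reference-level reading fits the sentence and gives the paired standard error.

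Further points stand in part:
- B has one response per patient, so a patient random intercept cannot be separated from residual error. It is an ANCOVA and fits the words mixed model poorly. Its interval is valid for the change conditional on the observed baselines and is too narrow only for the population mean change. The largest figures come from B.
- A is closer to a two-visit mixed model, and its effect is modest unless correlation is low. Part of its excess error reflects the choice of degrees of freedom: with 32 df, type I error is 8.4%, 6.6% and 5.7% at r = 0, 0.5 and 0.7.
- The plan does name the QLQ-C30 outcomes and ties the sample size to global health status. What is missing is the form of the response, not the instrument or scale.

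None of this supplies the missing contrast. That one sentence can lead to intervals of different width supports the need to specify the model.

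**Conclusion.** The gap holds on the text alone: no stated coefficient is the mean pre-post change in global health status for which 33 patients were calculated. The claim about the standard error is conditional. It applies if baseline score is a covariate, the target is the population mean change and ordinary model variances are used. Its size then depends on a correlation and a day-30 SD that the documents do not give, and runs from large (B at low correlation) to negligible (day-30 SD 25, r = 0.7).

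A reader might also infer that the sample size is wrong or that the study would miss a real effect. Neither follows. The figure of 33 reproduces, and a true 14-point change would usually still be detected. The harm is to interval width and error rate. As quality of life is a secondary aim beside a descriptive primary aim, severity is low to moderate.

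**What to change.** Rewrite the sentence in Section 6 to state:
- **Responses:** inclusion and day-30 scores, one row each.
- **Model:** a fixed visit effect, a patient random intercept (or an unstructured 2 × 2 covariance), no baseline score as covariate, and t-based degrees of freedom.
- **Estimate:** the day-30 minus inclusion contrast in global health status with its 95% CI, named as the estimate of the 14-point change.
- **Alongside:** the paired t result in complete pairs.
- **Separately:** visit by oncological treatment, in its own model.

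An alternative keeps baseline score as a covariate but uses a variance that allows for the sampled baseline mean. In the equal-SD simulations of B this gave type I error of 4.8%, 4.8% and 4.6% at r = 0, 0.5 and 0.7.

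The cost is wording only, with no new data. There are two downsides. Patients with only an inclusion score contribute under a missing-at-random assumption that early deaths may violate; the complete-pair result shows how much depends on this but does not remove it. If r is near 0, the random intercept is estimated at zero in about half of samples and the random-intercept version has type I error of about 5.6%, while the paired t stays at 5.0%. If the software offers no small-sample option for mixed models, the paired t interval provides one for complete pairs.
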